#### 4.6 DEVIATIONS FROM STUDY PROTOCOL

Any deviations from the study protocol should be notified to the sponsor and documented on study deviation forms.

### 5 MEDICAL DEVICE DESCRIPTION

#### 5.1 DEVICE INTENDED USE

Paralyzed people cannot interact with their environment, despite the cognitive competence, due to motor limitations. Existing communication devices on the market are expensive and cumbersome, and unfortunately most of these devices are not portable. Even if a patient can afford to purchase one of these products financially, he cannot use the device without the screen of a portable computer, so that these patients are left without many appropriate means of communication when they are in bed, on the move in a wheelchair, car, at a hospital, etc. This fact is truly limiting and isolating for the patients and they might even find themselves in a life-threatening situation without the ability to express this to those surrounding them.

The EyeControl device is a speech generating device based on eye-movement detection, used by patients with ALS (Lou Gehrig's Disease), and other "locked in" conditions for communicating with their loved ones and caregivers.

## 5.2 DEVICE DESCRIPTION

The EyeControl device is an eye-based communication device in the form of wearable glasses with connected infrared camera that tracks the pupil and translates blinks and movements into commands. The camera communicates with a small computer that transmits the eye movement into speaking/writing. For further details please refer to device investigator's brochure.

## 5.3 DEVICE OPERATIONS

### 5.3.1 General

The EyeControl device enables the following list of actions:

1. Calling for help.
  2. Choosing from a variety of predefined sentences.
  3. Free text speech - using the Android app.
- The user will navigate through the options and execute them using blinking and 4 pupil movements: up, down, right, left.
  - Fully supported in English and Hebrew.

### 5.3.2 Installation & Calibration

The device arrives ready for activation. The user/caregiver should plug it in to a battery or an electrical outlet and wait until the "All set" sound is spoken through the speaker. The calibration process begins several seconds afterwards.

The user will hear "Calibration" in earphone.

Then he will hear "1", "2", "3" which are corresponding to three stages of calibration.

We recommend the following:

- After the "Calibration" – the user should blink few times to allow the camera spot the area of interest – when he will hear "1" he can stop blink.
- After "1" he can look straight at the camera – to allow the camera to spot the pupil – when he will hear "2" he can stop look at the camera.
- After "2" he user can move his eye randomly to all sides – to allow the camera to understand the range of movement of the pupil. When the user hear the word "3" he can stop do that, and the calibration is actually over.

The whole calibration stage should take 5-10 seconds.

After calibration stage the user immediately gets to the main menu which is described in the next section.

There is no visual display for the device, but it can be described schematically in the following way:

words										
levels	directions	questions	hygiene	family	in hospital	in bed	clothing	general	actions	feelings
0-9	left, right,..., forward	why, who,..., where	tissue, toilet,...	father,..., grandson	nurse,..., doctor	light,...,tv	pants,...,shirt	yes, no,..., more, less	give, take,..., sleep	happy,...,frustrated

Chart 2: Navigation schema

To navigate between the words options, a user needs to look left or right.

To make a selection of a specific word, for example “father” the user need to look few times left or right (the menu is cyclic) until he hear “family” in the earphone, then he need to look down in order to hear “Father”. If he wants to say “Father” in the speaker he needs to blink to confirm.

Next to the words menu (look left or right) there are more menus which allow the user to connect to the application or to be in rest mode or to change settings.

application	rest mode	settings		
		toggle earphone language	toggle speaker language	toggle gender

Chart 3: The menus schema

- To choose any option that you hear- A blink.
- An "I need your help!" siren – 3 blinks (each blink should be about 0.25 seconds long). All three blinks should be executed in 4 seconds (default x = 4, can be configured in configuration file). If for example the user is making:
  - Blink1, Right, Blink2, Blink3 – that will count as two blinks (blink2 and blink3) If he will make another blink 4 seconds after blink2, a siren will be played.
- Going out of Rest Mode:
  - Looking Down- Center- Down- Center- Down- Center in 4 seconds.
- Getting in to Rest Mode: via menu or by making a sequence of
  - Blink-Up-Blink-Up in 4 seconds

### 5.3.3 Top Menu

- The **Settings** menu includes the following options
  - Toggle earphone language – select the language you will hear on earphone
    - English or Hebrew (other languages will be available in the future)
  - Toggle speaker language – select the language you and others will hear on speaker
    - English or Hebrew (other languages will be available in the future)
  - Toggle gender – select the gender of the voice heard on earphone and speaker
    - Male or Female

- **Rest mode**- A mode in which the application does not respond to the eyes' movements of the user. This mode allows the user to rest or look in different directions without activating the system, for example, in the middle of a treatment. In order to switch back from Rest Mode to regular Activation Mode, the user must look down quickly 3 times (Down- Center- Down- Center- Down) in a 4 seconds time frame. Outside of this sequence of gestures, there is another sequence that allows the user to express distress (3 quick blinks). These are the only two gestures sequences that are activated during Rest Mode. A partial execution of these commands will not be effective after 4 seconds since the beginning of the sequence.
- **Application** - Choosing the Application option results in trying to connect the device via Bluetooth, to a smartphone that went through Pairing in advance. In the case that the connection attempt is successful, the device goes from playing pre-recorded words/siren or settings menu mode to a mode in which eye gestures are sent to the app and there they're converted to letters and free speech. To return to the regular mode in which the user hears the pre-recorded words through a headphone/speaker, the companion will close the app on the smartphone.

#### **5.3.4 WORDS MENU**

The words menu includes more than 100 pre-recorded words in English or Hebrew (Based on the settings menu choice). The user can browse through the words in a group by looking left or right. The user can get out of a group by looking up or to get in the group by looking down.

The user first hears the words through the headphone only, and in order to play this word through the speaker the user has to blink.

#### **5.3.5 SWITCHING FROM THE WORDS TO OTHER MENUS**

To switch from words menu to the other options, the user must look up few times until he hears "words", only then he will be able to navigate to other options such as "application" or "rest mode" by looking left or right.

#### **CALLING FOR HELP**

Blinking 4 times at any stage of the execution will issue a call for help.

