## 1.7 STUDY ENDPOINTS

### Primary endpoint:

Assessment of the feasibility of the use of EyeControl device, measured by:

- **Ability to perform device features:**
  - Controlling the EyeControl's Joystick [measured by successful correct performance of over 70% of the gestures].
  - Controlling the Rest mode and Siren mode [measured by successful correct performance of over 70% of the gestures].
  - Testing the logic of the pre-defined sentences;
    - a. ability to say 10 pre-defined sentences [over 80% success rate];
    - b. Time - perform each sentence in less than 2 minutes – [over 80% success rate for all sentences].
  - Controlling the application and Free text features –words per minute, using the application Alphabet
- **Required Training time/ learning curve of;**
  - pre-defined device features [selected results after the 4th meeting compared with results results of previous meetings]
  - free speech [selected results after the 4th meeting compared with results after the 3rd meeting]
- **Usability** feedback (user experience) questionnaire completed by each user.

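### The help-call gesture is 3 blinks in two places and 4 in a third, although siren control is scored in the primary endpoint

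*Protocol*

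**What the plan says.** Section 5.3.1 lists a single help function ("Calling for help") as the first of the device's three actions. Three places then say how to trigger it:

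- Section 5.3.2, in the gesture list at its end, defines the siren as "3 blinks (each blink should be about 0.25 seconds long). All three blinks should be executed in 4 seconds". The length of the window is configurable, with 4 seconds as the default.
- Section 5.3.3, on rest mode, mentions "another sequence that allows the user to express distress (3 quick blinks") and says that a partly executed sequence lapses 4 seconds after it began.
- The unnumbered Calling for Help paragraph, after section 5.3.5, says "Blinking 4 times at any stage of the execution will issue a call for help". It gives no time window.

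Section 1.7 and the synopsis make "Controlling the Rest mode and Siren mode" a component of the primary endpoint, met when more than 70% of the gestures are performed correctly. Sections 4.2 and 4.3 ask the user to turn these modes on at meetings 1 and 2. They state neither the blink count nor the number of attempts.

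**The concern.** A performance endpoint needs one definition of a correct performance. Section 5.3 is the only part of the protocol that says what the siren gesture is, and it gives two answers. The trainer, the participant and the person completing the CRF could each follow a different paragraph.

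Two things are at stake. The first is scoring: the same recorded attempt can count as a success or a failure depending on which paragraph is applied. The second is attribution. Section 8 names both malfunction and use error as forms of device deficiency. If a participant makes the taught sequence and nothing sounds, the protocol cannot say which of the two occurred, and a feasibility study needs to know.

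This is a contradiction in the current text of a first-issue protocol. It is not a design choice, nor a detail that could be left to a statistical analysis plan, because the protocol itself fixes the gesture in two different ways.

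**Working it through.** There is no sample-size or power figure to reproduce; section 9 states that none was calculated. The check is mainly a comparison of texts.

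**Can the three rules describe different functions or modes?** No. Only one help function is described in the synopsis, section 1.3 and section 5.3.1. The four-blink rule is stated to apply at every stage, so it overlaps both the general three-blink rule and the rest-mode three-blink rule.

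**How would each attempt be scored?**

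| Attempt | Under 5.3.2 and 5.3.3 | Under Calling for Help |
|---|---|---|
| 3 quick blinks within 4 s | correct | incomplete |
| 4 quick blinks within 4 s | first three already satisfy the rule | correct |
| 4 slow blinks over more than 4 s | depends on whether three fall inside the window | correct as written (no window) |

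**What happens if teaching and software disagree?**

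- Three taught, four needed: the siren does not sound, and correct users are recorded as failing.
- Four taught, three needed: the siren probably sounds on the third blink. A fourth blink might then be read as a menu selection, since section 5.3.2 makes a blink the selection gesture. That is an inference, and it would not apply in rest mode. It would not be a failed siren.

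**Two smaller wording differences in the same place.**

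- Rest-mode exit is "Looking Down- Center- Down- Center- Down- Center in 4 seconds" in section 5.3.2, while section 5.3.3 ends the sequence on the third downward look. Both require three downward looks in 4 seconds. They differ only on whether the last return to centre must fall inside the window.
- In the worked siren example of section 5.3.2, a rightward look resets the count, so the sequence starts at the second blink. A closing blink placed 4 seconds after that one lies on the edge of the window. This reads as loose wording for a limit.

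**Illustration of size.** Assumptions, none of them in the protocol: each blink is detected independently with probability p, and an attempt is scored as a whole sequence. Expected success is then p³ for three blinks and p⁴ for four.

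| p | p³ | p⁴ | Against 70% |
|---|---|---|---|
| 0.85 | 0.614 | 0.522 | both fail |
| 0.90 | 0.729 | 0.656 | three passes, four fails |
| 0.95 | 0.857 | 0.815 | both pass |

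The thresholds are 0.7^(1/3) = 0.888 and 0.7^(1/4) = 0.915. The expected verdict differs only between them, a width of 0.915 − 0.888 = 0.027, or under 3 percentage points of per-blink detection.

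**The case against.** The strongest reply accepts the wording conflict and disputes its consequences.

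- **The software has one trigger rule, whatever the protocol says.** Comparing p³ with p⁴ compares two differently programmed devices. A reader might infer that the choice of definition alone flips the 70% verdict. The documents do not support that: they give no detection rate, and even in the illustration the flip needs p in a narrow band. This stands, and the figures remain illustrative only.
- **The unit may be the single gesture.** Sections 4.2 and 4.3 list a blink as a gesture in its own right. If the 70% is counted per blink, detection of 90% passes with three blinks or four. This stands as a further limit on the illustration.
- **A wrong count would probably show itself.** The siren is audible, users are guided on it at meeting 1 after a demonstration, and company representatives or trained staff attend each session. This lowers the chance that a wrong count persists. It does not settle how attempts made before the discovery are scored.
- **Other documents may govern.** Sections 3.4 and 5.7 refer to the Instructions for Use and section 5.2 to the investigator's brochure. Neither is at hand, so a single working definition may exist. But section 5.7 binds investigators to the protocol as well, and the protocol gives two rules.
- **Safety.** A reader might infer that participants are left with an unreliable emergency call. Section 6.2 answers this by restricting the pilot to people who can communicate without a device, and section 3.1 requires understandable speech. This stands.

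**Conclusion.** The point holds as an internal contradiction. Two paragraphs say three blinks and one says four for the same function, and that function is scored in the primary endpoint. At least one stated rule must be wrong, and the protocol does not say which governs training or scoring.

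Its weight is moderate. Only one direction, three taught and four required, clearly loses the siren. It would be too strong to say that the success rate reflects the document conflict whichever rule the software follows, because four quick blinks already contain three. The study is a descriptive proof of concept in up to 10 + 5 = 15 subjects with no hypothesis test, so no error rate is affected. What suffers is the interpretation of one primary component and the ability to separate user failure from device failure.

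The textual finding rests on no assumption beyond there being one help function. The numerical band rests on independent blinks and per-sequence scoring, both assumed. The rest-mode ending and the timing example are minor and would not justify a finding by themselves. The item should be fixed, but it is not one that must hold up the study.

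**What to change.** Before the first subject:

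1. Reconcile sections 5.3.2 and 5.3.3 and the Calling for Help paragraph with the software version under test, its configuration file and the Instructions for Use. State one blink count and one time window. This review does not say which count is right.
2. In the same edit, align the two rest-mode exit sequences and reword the worked timing example so that it agrees with the stated window.
3. Use the reconciled sequences in the training script and as the CRF definition of a correct siren or rest-mode activation. Say whether the 70% is counted per complete sequence or per single gesture.
4. For a failed attempt, record whether the defined sequence was actually performed, so that user error and device failure can be told apart.

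The cost is protocol and CRF wording plus one check of the configuration. It adds no burden for subjects and does not change the sample size or the schedule.

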#### **5.3.6 SOLVING INITIAL PROBLEMS**

- In case the user cannot hear words through the headphone, check the connection to the device.
- In case the user blinks and no sound is produced through the speaker, check the connection to the device. Also check that the speaker's battery is not empty (a light in the speaker is on).
- In case that one of the above issues was not resolve solved, check that the device is on (a blue light and a red light are on in the device's box).

- Check that the battery isn't empty. Recharge it if needed. If the battery is intact and the device still does not function properly, turn the device off and then turn it on.

In case turning the device off and on does not resolve the issue, make sure that the blue light is on inside the camera itself. If the issue is not resolved, please refer to the technical support section.

#### **5.4 MANUFACTURING, SUPPLY AND SUPPORT OF DEVICE**

The EyeControl device is manufactured by Eyefree assistive communication Ltd. (Ramat Gan, Israel).

The device is supplied packed in a box that will be brought by the company.

#### **5.5 DISTRIBUTION AND SHIPMENT**

The EyeControl device will be distributed to the investigational site following completion of regulatory clearance, including approval by the site's EC and training of the interventional staff.

Shipment of the study devices will be performed by Eyefree or their agents.

#### **5.6 TRAINING**

Each Investigator participating in the clinical trial and the associated clinical study staff will receive training on the clinical protocol, as well as the investigational device. Investigators will be trained on device characteristics; storage requirements; device application; device use; and warnings, precautions, and contraindications.

#### **5.7 ACCOUNTABILITY AND COMPLIANCE OF INVESTIGATIONAL PRODUCT**

Complete traceability records will be kept of all devices during the study. The device will be provided by Eyefree Ltd., bearing required labeling. Device number will be documented in subject medical records, CRF and in center log.

Each clinical investigator will be responsible for the safe storage with restricted access of the investigational materials in their possession, thereby preventing use of any materials by any persons not participating in the study.

After completion of the study, all unused devices must be returned in their original package to Eyefree Ltd.

All investigators will be responsible for using the products according to the instruction for use and protocol and maintaining product inventory and records.

#### **5.8 DEVICE FAILURES, MALFUNCTIONS AND MISUSE**

Investigators are instructed to report all possible device failures, malfunctions or misuse observed during the course of the trial (refer also to section 8, Device Deficiency). These incidents will be documented in the case report form provided and sent by fax or e-mail to the monitor within two working days.

#### **5.9 CONTRA-INDICATION**

Only per exclusion criteria.

## 6 RISK BENEFIT ANALYSIS

The EyeControl device is designed according to international standards for medical devices. Compliance with these standards ensures that the device can be used safely in human beings. This study is intended to provide further data on the device safety and performance.

### 6.1 RISK MITIGATION MEASURES

Several mitigation measures were taken to minimize the possible risks;

#### 6.1.1 Mechanical Tests

The device was tested in the SII in a radiation test in order to check that the Infra Red radiation of the device doesn't cause damage to the eye of the pupil.

The conclusions were that the device is safe in the "Infra Red" aspect. The Led light is classified as Exempt Group (For: Actinic UV, Near UV, Blue light, Blue light small source, Retinal thermal, Retinal thermal, weak visual stimulus, IR radiation, eye)

For detailed results refer to the device Investigator Brochure.

#### 6.1.2 Software validation tests

A software validation was made by Med-Dev Design Ltd. The validation test included: ATP and ATR tests. The tests were successfully completed without any bugs or other unexpected results.

For detailed results refer to the device Investigator Brochure.

## 6.2 RISKS

**1. Infra-Red Radiation:** the cameras has 4 LEDs with 850 nm wave length- and the risk is that the waves transmitted will heat the eye and by that will cause damages to the user- **This risk was tested by the SII .**

**2. Electricity damages:** the hardware of the device is composed from a battery, Odroid U3 and a speaker which can all go through an electricity damage. All the products are off the shelf products, **bearing CE mark.**

**3. Parts falling apart:** The device is not a one product device yet- so pieces of the device can be split- this risk may cause damages in a very specific conditions. – **We are creating a custom made boxes (3D printer) for the battery and the additional hardware which shouldn't be exposed.**

**4. True Emergency situations** – In cases the user truly needs to call for help and the device doesn't work. **Our pilot involves only users who can communicate without any communication device.**

**5. Allergy to the device** - In case the user has allergy to the device material (plastic, wires etc') in this case the patient will be switched.

Anticipated clinical risks to the participants, based on the above hazards may be (but not limited to); headache, nausea or dizziness caused by the multiple required eye-movements, local irritation due to allergy to device materials (glasses), burning sensation in the eyes.

### 6.3 BENEFITS

Based on compliance with standard requirements, the risk of occurrence of adverse events is not expected to be greater than the risk reported for other devices available in the market today. However, as the device is investigational, this study is intended to validate this. All adverse events reported will be recorded.

No direct benefit to the subject is expected in this study. Information gathered in this study will contribute to the development of the EyeControl solution which in the future may be more beneficial for the subjects with the same indication for treatment, when compared to the available solution on the market.

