## 1 INTRODUCTION

### 1.1 BACKGROUND-ALS

Amyotrophic Lateral Sclerosis (ALS, also known as Lou Gehrig's disease) is an adult-onset, fatal neurodegenerative disease. The disease is characterized by degeneration of motor neurons in the primary motor cortex, brainstem and spinal cord, leading to progressive weakness and atrophy of voluntary skeletal muscles. It is recognized as a multi-system disorder. In about a quarter of ALS patients, the disease is associated with subtle cognitive deficits.

The majority of patients die within 3-5 years from disease onset, usually from respiratory failure. Only about 10% of the patients survive for more than a decade.

ALS exhibits phenotypic heterogeneity. Most ALS cases are sporadic, with unknown etiology, whereas 10-15% are familial with clear genetic background – both types are clinically indistinguishable and share several pathogenetic pathways. The incidence of sporadic ALS is 1-2 per 100,000 person-years with an estimated lifetime risk of 1 in 400. The mean age at onset for sporadic ALS is 58-63.

There is no cure for ALS. Riluzole is the only FDA approved drug – which appears to prolong ALS survival by 3 months on average.

Almost all people with amyotrophic lateral sclerosis (ALS) experience a motor speech disorder, such as dysarthria, as the disease progresses. At some point, 80 to 95% of people with ALS are unable to meet their daily communication needs using natural speech.

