#### 1.5 STUDY JUSTIFICATION

The justification for the experiment is based on the fact that the group of people tested are cognitive in the same status of the ALS patients that will be the final user of the product. Moreover, the product is being tested on an early stage ALS patients.

In order to minimize possible risks prior to clinical application, Eyefree Ltd. designed and performed verification and validation tests for the EyeControl device. The testing

included aspects of the device's clinical safety, production and software and quality assurance.

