## 1.6 STUDY OBJECTIVES

To demonstrate the safety and feasibility of the EyeControl device in healthy volunteers, and ALS patients in early stages.

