## 2 STUDY DESIGN

This will be a single center, single arm, open label, prospective study.

The study will be conducted in 2 enrollment stages. Initially, up to 10 healthy volunteers will be recruited and go through a short training for the use of the device followed by actual controlled use of several hours. In the second stage, up to 5 early stage ALS patients will be recruited and go through the same steps of training and device use.

Any feedback or safety concerns raised during the first stage of recruitment of healthy volunteers will be considered before moving forward to the second group of ALS patients.

The overall duration of participation for each subject will be up to 3 weeks.

The place: Rambam health care campus.

Each subject will go through a series of 4 meetings (2 meetings per week), and up to 3 hours per meeting. Meeting will be accompanied by company representatives and/or trained study team for support and guidance in each session..

Procedure will consist of an introduction and demonstration of the device features followed by actual use of the device by each subject (including control of gestures, use of menus, activation of pre- defined modes and writing full sentences). User feedback/questionnaire will be completed after the 2nd and 4th session.

The user's ability to perform each of the pre-defined tasks will be measured in each session. In addition, success rate and measured time for completion of pre-defined tasks, collected after the 4th session, will be compared to the success rate and times collected in previous sessions.

For detailed study procedures refer to section 4, as well as appendix A.

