## **9 STATISTICAL ANALYSIS PLAN**

The planned sample size is considered adequate for this study. No formal sample size calculation was performed for this study, as the study was not expected to show statistical significance or statistical power.

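### Section 6.3 says the study will validate that adverse-event risk is no greater than with marketed devices, which a single-arm study of at most 15 subjects with no benchmark cannot do

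*Protocol*

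**What the plan says.** Section 6.3 makes a comparative statement: "the risk of occurrence of adverse events is not expected to be greater than the risk reported for other devices available in the market today". The next sentence gives the study's relation to it: "However, as the device is investigational, this study is intended to validate this".

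The objective in Section 1.6, which also stands in the Synopsis, is: "To demonstrate the safety and feasibility of the EyeControl device in healthy volunteers, and ALS patients in early stages".

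The design in Section 2 is described so: "This will be a single center, single arm, open label, prospective study". On size it says "Initially, up to 10 healthy volunteers will be recruited", followed by a second stage of up to 5 early-stage ALS patients. No minimum is set for either group. Section 4 gives four meetings of up to 3 hours over two weeks, and the Synopsis states that there is no follow-up.

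Safety is the secondary endpoint in Section 1.7, a count of adverse events related to the device. It has no threshold, reference rate or margin. Section 1.3 compares marketed eye trackers on function, calibration and price, and gives no adverse-event rate for any of them.

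Two other places are more modest. Section 9 says that no sample size calculation was made and that significance and power were not expected. The opening paragraph of Section 6 says only that the study should add to what is known about the device's safety and performance.

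**The concern.** To validate that one risk does not exceed another needs three things: the other risk as a number or a concurrent arm, a margin that says how much excess is tolerable, and enough subjects to exclude that excess. The protocol has none of the three. The verb in Section 6.3, and to a lesser degree the aim of demonstrating safety, therefore gives the study a property that its design lacks.

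What is at stake is the conclusion that the study may draw. The most favourable outcome is that nobody has a device-related event. Under the present text that outcome could be presented as confirming safety comparable to marketed devices, although it would be compatible with sizeable event rates, above all in the ALS patients for whom the device is meant.

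**Working it through.** **Inputs.** All come from the protocol: at most 10 healthy volunteers and at most 5 ALS patients, single arm (Section 2); four meetings of up to 3 hours, so at most 4 × 3 = 12 hours per subject (Section 4), part of which is introduction and demonstration; no follow-up (Synopsis); no reference rate or margin (Sections 1.3, 1.7, 6.3 and 9). There is no figure of the plan to reproduce, because Section 9 says that no calculation was made.

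**Unit.** The endpoint in Section 1.7 counts events. The limits below are for the proportion of *subjects* with at least one device-related event, the natural binomial quantity. They are not limits for the event count.

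**Step 1: best case, zero subjects with an event.** The two-sided exact (Clopper-Pearson) 95% upper limit is 1 − 0.025^(1/n).

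| Group | n | 0.025^(1/n) | Upper limit |
|---|---|---|---|
| Both groups | 15 | 0.782 | 21.8% |
| Healthy volunteers | 10 | 0.692 | 30.8% |
| ALS patients | 5 | 0.478 | 52.2% |

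One-sided 95% limits, 1 − 0.05^(1/n), are 18.1%, 25.9% and 45.1%. The row for 15 assumes the same rate in both groups and is shown only as the most favourable reading. If fewer subjects are enrolled, all limits are wider.

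**Step 2: chance of seeing no event when the true rate is p**, that is (1 − p)^n. The values of p are assumptions.

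| p | n = 15 | n = 5 |
|---|---|---|
| 5% | 0.95^15 = 46% | 0.95^5 = 77% |
| 10% | 0.90^15 = 21% | 0.90^5 = 59% |
| 20% | 0.80^15 = 4% | 0.80^5 = 33% |

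**Step 3: subjects needed, with zero events, to exclude a rate p.** On the same two-sided convention, this is the smallest n with (1 − p)^n ≤ 0.025. For p = 10%, ln 0.025 / ln 0.90 = 35.01, so 36 subjects. For p = 5%, ln 0.025 / ln 0.95 = 71.9, so 72 subjects. With a one-sided 95% limit the numbers are 29 and 59.

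**Step 4: would a benchmark added later rescue the claim?** Assume a fixed benchmark b and a margin m, neither of which the protocol gives. Take an exact one-sided 5% test of the rate b + m, with the true rate equal to b.

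- b = 5%, m = 10 points, n = 15: zero events has probability 0.85^15 = 0.087 under the null. This exceeds 0.05, so no result can pass.
- b = 10%, m = 10 points, n = 15: 0.80^15 = 0.035, so only zero events passes, and the power is 0.90^15 = 21%.
- Over b from 5% to 30% and m of 10 or 15 points, power at n = 15 ranges from 0 to 46%.
- At n = 5 the power is 0 throughout. Even at the highest tested null rate, 45%, 0.55^5 = 0.0503 exceeds 0.05.
- The smallest n that first reaches 80% power is 59 to 143 for a 10-point margin and 30 to 70 for a 15-point margin.

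**The case against.** The strongest reply is that Section 6.3 is narrative. It sits in the risk-benefit chapter, and no objective, endpoint or statistical statement commits to a comparison with marketed devices. The sentence after it promises only that adverse events will be recorded. The Synopsis labels the study first in human and proof of concept, Section 9 openly disclaims power, and an aim of demonstrating safety and feasibility is common wording at this stage. Much of this stands, and it limits the point to a fault of wording. It does not remove the point. The sentence states what the study is intended to do, and it disagrees with Section 9 and with the opening of Section 6. A separate statistical analysis plan could add tables or even a benchmark, but not a comparator arm or more subjects.

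A reader might infer more than the documents support:

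- *That the sample size is wrong.* Section 9 says "The planned sample size is considered adequate for this study" and then disclaims significance and power. For a first-in-human proof of concept these statements are compatible, and no larger study is called for.
- *That the groups will be pooled, so that healthy volunteers mask the ALS result.* The protocol plans no pooled figure. It defines the groups separately and enrols them in separate stages.
- *That the sponsor will report validated safety.* Section 12.5 promises an integrated report and prescribes no such conclusion. The wording permits the claim but does not commit to it.
- *That Section 1.5 carries safety results over from healthy volunteers to ALS patients.* It speaks of cognitive status, not of event rates, and adds that ALS patients are tested too. Its tension with the subtle deficits mentioned in Section 1.1 is a separate matter.

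**Conclusion.** The point holds as a correction to the stated safety aim. The design cannot validate the comparison in Section 6.3: without a reference rate and a margin it cannot be tested at any sample size, and with illustrative ones the planned numbers fall well short. Even a result without any event leaves rates up to 22% (15 subjects), 31% (10 healthy volunteers) and 52% (5 ALS patients) unexcluded, over at most about 12 hours per subject.

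The upper limits assume full enrolment, independent subjects and the two-sided exact 95% convention, and they refer to subjects with an event. The limit for 15 also assumes a common rate. The rates in Steps 2 and 3 and the benchmarks and margins in Step 4 are illustrations; the conclusion does not depend on any one of them. The change is small, but it alters what the study may conclude and should be made.

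**What to change.** 1. In Section 6.3, delete the sentence on validation, or restate it, for example: *This is an expectation, which the present study is not designed to test.*
2. Bring the safety part of the objective into line with the opening of Section 6, for example: *to collect preliminary, descriptive safety data in each group*. Change it in both the Synopsis and Section 1.6; editing only one would create a new inconsistency.
3. State, in Section 9 or with the secondary endpoint, that safety conclusions are descriptive. They should rest on the number of subjects with a device-related event in healthy volunteers and in ALS patients, each with an exact 95% interval, beside the count of events that Section 1.7 already names.

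The cost is a few sentences and one short table, with no added subjects, visits or procedures. The downside is a more modest safety claim. If the comparison with marketed devices is wanted as a claim, it needs a sourced benchmark, a margin and a separate study sized for them.
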